Klinika Położnictwa, Perinatologii i Neonatologii CMKP

SPZOZ - Szpital Bielański im. ks. Jerzego Popiełuszki

[name]

[contact] – [name]

Kierownik Kliniki: dr hab. n. med. [name], prof. CMKP

---

1.03.2022

Comparison of the Efficacy of Emergency Two-level and Single Cervical Cerclage in Cervical Insufficiency in the Second Trimester of Pregnancy - Multicenter Prospective Randomized Trial

Cervical Occlusion Two-level Stitch Application (COSA)

Study Protocol and Statistical Analysis Plan

Unique Protocol ID: nr 5/2024

This is an open-label, multicentre, prospective, randomised controlled trial (RCT).

Women

diagnosed with cervical insufficiency with fetal membranes visible through open internal os between

16+0 and 25+6 weeks of gestation will be included to the study. The inclusion criteria consist of

singleton pregnancy, gestational age 16+0 to 25+6 weeks, live fetus. The exclusion criteria are:

- preterm rupture of membranes,
- vaginal bleeding,
- regular uterine contractions,
- maternal fever,
- diagnosed fetal genetic disorders,
- diagnosed major fetal anomalies,
- multiple pregnancy,
- congenital uterine anomalies,
- fetal demice,
- maternal leukocyte count >20 million/microliter,
- maternal serum C-reactive protein concentration > 20 mg/L.

Each patient will have a vaginal swab for aerobic and anaerobic bacteria and fungi culture, as well as

for mycoplasmas, chlamydia and ureaplasma performed. Each patient will be treated with progesterone

(vaginally 2 x 100 mg per day) and empirical antibiotic therapy (ceftriaxone 2.0 g iv + clarithromycin 2 x 500 mg po + metronidazole 3 x 500 mg iv for 7 days). If specific pathogens will be detected, the

antibiotic therapy will be modified according to the antibiogram. If the diagnosis of cervical insufficiency will be made >23 weeks of gestation a single course of corticosteroid therapy will be

administered (betamethasone 2 x 12 mg im). Indomethacin will also be administered for 48 hours

(starting the day of cerclage administration, indomethacin 2 x 75 mg po for 48 hours). In the single-level

cerclage arm McDonald suture will be administered. In the double-level cerclage arm two separate

sutures analogous to McDonald technique will be placed, one above the other approximately 1 cm

higher. After randomization in the operating theater under regional anesthesia, after vaginal disinfection and visualization of the cervix, McDonald cerclage will be administered. In case of fetal membranes bulging to the vagina the patient will be placed in the Trendelenburg position with filling the bladder with saline and / or amnioreduction. In double-level cerclage arm two separate sutures analogous to the McDonald technique will be places, one approximately 1 cm higher above the other.

After the operation patients will receive standard perinatal care and will be followed up until miscarriage or delivery. The time and mode of delivery, the occurrence of complications related to the

cerclage placement and neonatal outcomes will be analyzed.

In the only randomized trial evaluating the effectiveness of rescue sutures in comparison to conservative management and bed rest, the rate of deliveries before 34 weeks of gestation was 53%.

Assuming a reduction of deliveries before 34 weeks to 20%, based on the power analysis of the test, the

size of each group was calculated for 39 patients.

After ending recruitment and collection of data, statistical analysis will be performed. Variables will be described as median, interquartile range or number and percentage. The Mann–Whitney test and the Fisher’s exact test will be used for the statistical analysis. p-values < 0.05 will be considered significant.

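### The leukocyte exclusion threshold is written in a unit that makes it unattainable, so read literally it excludes nobody

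*Combined protocol and SAP*

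**What the plan says.** The combined protocol and SAP has one list of exclusion criteria, in its opening description of the design. It has 11 entries, and two carry a numeric limit: "maternal leukocyte count >20 million/microliter" and "maternal serum C-reactive protein concentration > 20 mg/L". A further entry, "maternal fever", has no number attached.

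The leukocyte count is mentioned nowhere else. There is no second unit, conversion, laboratory range or footnote. The multiplier and the volume unit are both written out as words, so a superscript or symbol lost when the PDF was read is an unlikely explanation.

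The trial is open-label and multicentre, so the criterion has to be applied at more than one site. The closing paragraph speaks of the end of recruitment as a future step: "After ending recruitment and collection of data, statistical analysis will be performed". The document does not say whether screening has started.

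**The concern.** A numeric exclusion has to be usable as written. A limit of twenty million leukocytes per microlitre looks too high to be reached in any blood sample. If so, the line removes nobody, and exclusion rests on the other ten criteria.

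Screening staff then have two options: apply a rule that never triggers, or replace it silently with a value the protocol does not contain. In a multicentre trial, sites could differ in which they choose. Where a site does substitute a value, its eligibility decisions cannot be audited against the protocol text. Who is eligible is what is at stake; no mechanism that would favour one arm has been identified.

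**Working it through.** **Is there a figure to reproduce?** The threshold is a stated criterion, not a derived figure, so the plan offers no calculation of it. The one calculated figure in the document is the sample size ("size of each group was calculated for 39 patients"), based on rates of 53% and 20%. It reproduces as 39 per arm with a two-sided 0.05 level, 80% power and a continuity correction; sidedness, power and the correction are assumptions, as the document does not state them. The leukocyte threshold does not enter that calculation.

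**Inputs**
- From the exclusion list: 20 million per microlitre = 20 x 10^6 per microlitre.
- Unit identities: 1 L = 10^6 microlitres; 1 microlitre = 10^9 fL.
- Mean leukocyte volume: not in the document, so treated as an assumption and varied.

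**Step 1. Conversion to a per-litre count**

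20 x 10^6 per microlitre x 10^6 microlitres per litre = 2 x 10^13 per litre = 20,000 x 10^9/L.

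**Step 2. Largest mean cell volume that fits**

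Maximum mean volume = 10^9 fL / (20 x 10^6 cells) = 50 fL. This allows no plasma, no red cells and no gaps. As a sphere, 50 fL has a diameter of (6 x 50 / pi)^(1/3) = 4.57 micrometres.

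**Step 3. Sensitivity to the assumed mean volume**

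Share of sample filled = volume (fL) x 20 x 10^6 / 10^9.

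| Assumed mean volume (fL) | Cell volume / sample volume |
|---|---|
| 30 | 0.6 |
| 50 | 1.0 |
| 100 | 2.0 |
| 200 | 4.0 |
| 400 | 8.0 |
| 500 | 10.0 |

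Above 50 fL the cells would need more room than the sample has. Below 50 fL the count is not ruled out by volume alone, but at 30 fL leukocytes would still fill 60% of the sample.

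**Step 4. What a 1000-fold slip would imply**

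For a written value of N million per microlitre, correct one element at a time by a factor of 1000:
- the number: (N/1000) x 10^6 per microlitre = N x 10^3 per microlitre;
- the multiplier: N x 10^3 per microlitre;
- the volume unit: N x 10^6 per millilitre = N x 10^3 per microlitre.

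All three give the same concentration, 1/1000 of the one written. Sites making any one of these corrections would therefore reach the same rule. A slip of another size would not: reading the volume unit as litres changes the concentration by a factor of 10^6. Nothing in the document says which element is wrong or how large the slip is.

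**Step 5. Share of the eligibility rules affected**

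1 of 11 exclusions, and 1 of the 2 with a numeric limit.

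**The case against.** The strongest reply is that this is an obvious unit slip with little practical consequence. An absurd number is more likely to be noticed and queried than a plausible wrong one. Sites that make a 1000-fold correction end up with the same rule. Harm therefore needs a site that applies the line literally or corrects it differently, and the document gives no sign of either. Fever and C-reactive protein remain as separate exclusions. The criterion governs entry to both arms alike, so no bias between them follows. Finally, calling the threshold unattainable relies on a cell volume the document does not supply.

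Most of this stands, and it limits the impact. Differing application across sites is possible but not shown. The number of women who would be excluded on leukocyte count alone is unknown and could be small. The conclusion that nobody is excluded describes the literal reading; it is not an observed effect, and it depends on the volume assumption.

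None of it makes the line correct. The protocol lists leukocyte count as a criterion in its own right, and as written that criterion adds nothing to the others. That readers may guess the intended value does not remove the fault, because the document gives them no means of confirming the guess.

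**Conclusion.** The concern holds. The conversion and the 50 fL bound are exact. The further conclusion, that zero women are excluded by this line when it is read literally, rests on one assumption from outside the document: a mean leukocyte volume above 50 fL.

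This is a fault in an operative eligibility rule and should be fixed. It is not a fault in the randomised comparison: no effect on either arm, on the 39 per group or on the planned tests is shown. How many women are affected in practice cannot be derived. A 1000-fold unit slip is consistent with the text but remains unconfirmed.

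**What to change.** The sponsor should confirm the intended value and unit, restate the criterion in an attainable unit that site laboratories report, and notify every site. If any women have already been screened or enrolled, their leukocyte results should be checked against the confirmed threshold. The choice of threshold belongs to the sponsor, and none is proposed here.

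The cost is a one-line protocol correction and a note to sites, plus a check of records only if screening has begun. No extra patients or procedures are needed.

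### Bulging of the membranes separates two presentations in the protocol but is not specified as a baseline variable or used in the analysis, which gives up some precision and protection against chance imbalance

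*Combined protocol and SAP*

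**What the plan says.** The sections of the combined protocol and SAP are unnumbered. Four places bear on this point.

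- **Eligibility paragraph.** Women qualify if "diagnosed with cervical insufficiency with fetal membranes visible through open internal os between" 16+0 and 25+6 weeks. This does not separate membranes that are merely visible from membranes that have come down into the vagina.
- **Operative procedure paragraph, handling of bulging.** "In case of fetal membranes bulging to the vagina the patient will be placed in the Trendelenburg position", combined "with filling the bladder with saline and / or amnioreduction". Bulging is thus a distinct state that changes what is done in theatre.
- **Operative procedure paragraph, sequence.** "After randomization in the operating theater under regional anesthesia, after vaginal disinfection and visualization of the cervix, McDonald cerclage will be administered". Every cervix is seen, but in this sentence the viewing follows randomisation. The opening description calls the trial open-label.
- **Follow-up and closing statistical paragraphs.** The list of what will be analysed runs "The time and mode of delivery, the occurrence of complications related to the" suture placement, and then neonatal outcomes. The methods sentence is "The Mann–Whitney test and the Fisher’s exact test will be used for the statistical analysis". No baseline covariate, stratification factor or adjusted analysis is named.

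**The concern.** The protocol's own text distinguishes two presentations by what the operator must do. It is reasonable to expect that a woman with bulging membranes is at higher risk of early delivery, although the documents give no figure for this. If bulging is prognostic, two things follow in a trial of 78 women.

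- The arms may differ by chance in the share of women with bulging membranes. The plan has no pre-specified way to allow for that.
- An unadjusted test treats the outcome variation explained by bulging as noise, so some precision is lost.

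The timing of any remedy matters. In an open-label trial, an adjustment chosen after the imbalance and the outcomes have been seen would carry little weight.

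**Working it through.** **Inputs from the documents:** delivery before 34 weeks 53% and 20%; 39 women per group; significance at p < 0.05; Fisher's exact test.

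**Assumptions, because the documents give no figure:** two-sided test; 80% planned power; prevalence of bulging q = 50% (30-70% for the imbalance step); odds ratio of bulging for delivery before 34 weeks from 1 to 6, the same in both arms.

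**1. The plan's own sample size.** n = [1.96·√(2·0.365·0.635) + 0.8416·√(0.53·0.47 + 0.20·0.80)]² / 0.33² = (1.334 + 0.538)² / 0.1089 = 32.2. With continuity correction, n' = (n/4)·[1 + √(1 + 4/(n·0.33))]² = 8.05 × 4.72 = 38.02, rounded up to **39**. The stated figure reproduces. Exact Fisher power at 39 per group is 81.3%.

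**2. How often imbalance arises.** The arm difference in the proportion bulging has SD √(2q(1−q)/39): 11.3 points at q = 50%, 10.4 points at 30% or 70%. Exact binomial probabilities over 30-70% prevalence:

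| Imbalance of at least | Probability |
|---|---|
| 10 points | 39-43% |
| 15 points | 17-21% |
| 20 points | 6-9% |

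If the number of women with bulging membranes is instead fixed and split 39/39, the 15-point figure depends on whether that number is odd or even: 17% with 39 such women but 26% with 38 or 40; 23% with 26 but 14-15% with 25 or 27. It should be read as roughly 14-26%, not as a precise value.

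**3. What an imbalance does to the estimate.** Stratum risks are solved so that each arm keeps its design rate at q = 50%. The shift is the imbalance times the mean of the two within-arm risk gaps.

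| Odds ratio | Control, not bulging / bulging | Experimental, not bulging / bulging | Shift for 15 points |
|---|---|---|---|
| 2 | 44.5% / 61.5% (gap 17.1) | 14.6% / 25.4% (gap 10.9) | 0.15 × 14.0 = 2.1 points |
| 4 | 36.4% / 69.6% (gap 33.2) | 9.8% / 30.2% (gap 20.5) | 0.15 × 26.8 = 4.0 points |

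The design difference is 33 points.

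**4. Power with 39 per arm.** Simulation at q = 50%, 53% versus 20%; Mantel-Haenszel without continuity correction.

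| Odds ratio | Fisher | Mantel-Haenszel, unstratified | Mantel-Haenszel, stratified by bulging |
|---|---|---|---|
| 1 | 81% | 87% | 87% |
| 2 | 81% | 87% | 88% |
| 4 | 81% | 87% | 90% |
| 6 | 81% | 87% | 91% |

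Separate simulation runs put Fisher at 81-82%. The step from Fisher to unstratified Mantel-Haenszel is worth 5-6 points and makes no use of bulging. Bulging itself adds 0 to about 4 points.

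**5. False-positive rate.** With both arms at 53%, Fisher rejects in about 3% of trials and the stratified test in 4.8-5.4%. Among trials with an imbalance of at least 20 points, and an assumed excess risk of 20-40 points with bulging, Fisher's rate is about 4-7.5% and the stratified test's about 4-6%.

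**The case against.** The strongest reply is that an unadjusted test in a randomised trial is valid. Chance imbalance is already covered by the test's error rate, Fisher's overall false-positive rate is about 3%, and a shift of 2-4 points is small beside a 33-point design difference. All of that stands. It limits the point to precision and protection against imbalance, and makes adjustment an improvement rather than a repair.

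Four stronger readings are tempting, and the documents do not support them.

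- **That bulging is not recorded.** The document lists no baseline data of any kind, so its silence shows only that the item is not specified. Sites may well note it.
- **That the comparison is biased.** Randomisation rules out systematic imbalance.
- **That using bulging lifts power from 81-82% to 90%.** Most of that rise comes from leaving Fisher's conservative test.
- **That a box ticked when the cervix is viewed in theatre would do.** The operative paragraph puts that view after randomisation. In an open-label trial the judgement could be influenced by knowledge of the arm, and adjusting for it could introduce bias that is not there now.

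What remains is that the plan separates two presentations and never uses the distinction, and that using it properly costs almost nothing: if bulging is not prognostic, power is unchanged (87% against 87%).

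**Conclusion.** The point holds as one about precision and chance imbalance. The planned comparison is valid but leaves out a feature that the protocol itself treats as distinct. Stratifying by bulging adds 0 to about 4 points of power for odds ratios of 1 to 6, and corrects a shift of about 2-4 points when the arms differ by 15 points (odds ratio 2 to 4). An imbalance that large has a chance of roughly one in five under 30-70% prevalence.

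A reader might infer that imbalance is likely to overturn the result. The figures do not show that: the shift would matter mainly if the true effect were well below 33 points or the p-value close to 0.05.

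The sizes rest on assumed prevalence and odds ratios, and on a two-sided test. Gestational age at enrolment is proposed as a second factor because eligibility already requires it and spans 16+0 to 25+6 weeks; its gain has not been quantified.

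**What to change.** 1. Add one case-report-form item, membranes bulging into the vagina (yes/no), with a one-line definition. Complete it at the diagnostic or eligibility examination, before randomisation.
2. Before outcomes are analysed, pre-specify that the primary analysis of delivery before 34 weeks, the endpoint on which the trial was sized, is adjusted for bulging and gestational age at enrolment. Choose one method in the SAP: Mantel-Haenszel strata, with gestational-age bands fixed in advance, or a logistic model reported as a standardised risk difference with 95% CI.
3. Keep the unadjusted Fisher test as a sensitivity analysis.
4. For women already enrolled, use only bulging status documented before randomisation. Flag values taken from operative notes as post-allocation, and use them in a sensitivity analysis only.

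Eligibility, treatment and the 39 per group do not change. The cost is one form item, slightly more analysis work, and incomplete bulging data for women enrolled before the change.

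### The only complication outcome is limited to events related to the cerclage, in an open-label trial with no event list, definition of relatedness or blinded assessor

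*Combined protocol and SAP*

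**What the plan says.** The document has no numbered sections, so places are given by paragraph.

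- **Opening design statement:** "This is an open-label, multicentre, prospective, randomised controlled trial (RCT".
- **Operative procedure paragraph:** the arms differ in the suture itself. "In double-level cerclage arm two separate sutures analogous to the McDonald technique will be places, one approximately 1 cm higher above the other".
- **Follow-up paragraph:** "After the operation patients will receive standard perinatal care and will be followed up until miscarriage or delivery". The outcome sentence that follows lists the time and mode of delivery, then "the occurrence of complications related to the" and, completing the phrase, "cerclage placement and neonatal outcomes will be analyzed".

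Only the complication outcome in that sentence carries the words *related to*. Time of delivery, mode of delivery and neonatal outcomes carry no such limit.

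The document does not say which events count as complications, what makes one related, over what period they are counted or who decides. It mentions neither blinded nor independent assessment, and no tabulation of complications regardless of cause. These gaps do not fall at a redaction or a missing figure.

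**The concern.** The arms differ in the very procedure whose causal role would have to be judged, so attribution is tied to allocation. A clinician who knows that a second, higher suture was placed may be readier to blame it for a later membrane rupture, or less ready if he or she favours the technique. The bias could run either way.

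The document itself suggests that the events are ambiguous. Its exclusion list names ruptured membranes, vaginal bleeding, regular contractions and maternal fever, all of which can therefore be present before any suture is placed. When one of them appears after surgery, disease and procedure are both plausible causes. Amnioreduction, which the operative paragraph allows when membranes bulge, adds a third. Follow-up to miscarriage or delivery can be long, and late events are harder to attribute.

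Randomisation already separates the effect of the second suture from background events. A relatedness filter therefore adds a subjective step that the comparison between arms does not need. At stake is the maternal and procedural harm comparison, which has to be weighed against any benefit of the second suture.

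**Working it through.** **1. The plan's own figure.** The sample-size paragraph takes a comparator rate from a cited trial ("the rate of deliveries before 34 weeks of gestation was 53" per cent), assumes 20% with the new technique, and states that the "size of each group was calculated for 39 patients". Power and sidedness are not stated; I assume 80% and two-sided 0.05. With the mean rate (0.53 + 0.20)/2 = 0.365 and difference 0.33:

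n = [1.960 × √(2 × 0.365 × 0.635) + 0.842 × √(0.53 × 0.47 + 0.20 × 0.80)]² / 0.33² = 32.2, rounded up to 33.

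With continuity correction: n = (32.2/4) × [1 + √(1 + 4/(32.2 × 0.33))]² = 38.0, rounded up to 39.

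The stated 39 is reproduced. It concerns delivery before 34 weeks and is not in question; it fixes the arm size used below. No figure is stated for complications.

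**2. A single data set.** Assume that 9 of 39 women in each arm (23%) truly have a listed event, so there is no real difference. All 9 are counted as related in one arm and k in the other. The two-sided Fisher test, the plan's test for percentages, gives:

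| Counted as related | Rates | Share attributed in second arm | Fisher p |
|---|---|---|---|
| 9 v 9 | 23% v 23% | 100% | 1.00 |
| 9 v 5 | 23% v 13% | 56% | 0.38 |
| 9 v 4 | 23% v 10% | 44% | 0.22 |
| 9 v 3 | 23% v 8% | 33% | 0.11 |
| 9 v 2 | 23% v 5% | 22% | 0.047 |

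For the last row there are 11 counted events among 78 women. The p-value is 2 × Σ C(39,x)·C(39,11−x)/C(78,11) over x = 9, 10, 11, which is 2 × (0.0202 + 0.0032 + 0.0002) = 0.047.

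**3. Over repeated trials.** If an event occurs with true risk p and is counted with probability a, the counted risk is p × a. Summing exact binomial probabilities over all tables with two-sided Fisher p < 0.05, at 39 per arm:

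| Assumed true risk (one v two sutures) | Assumed share counted | Counted risk | Chance of p < 0.05, all events | Chance of p < 0.05, counted events only |
|---|---|---|---|---|
| 30% v 30% | 40% v 80% | 12% v 24% | 2.7% | 20.2% |
| 20% v 20% | 40% v 80% | 8% v 16% | 2.8% | 10.7% |
| 15% v 30% | 100% v 50% | 15% v 15% | 27.1% | 2.5% |

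The first two rows create a difference where none exists; the third hides a real one. Every event and attribution rate here is an assumption. The tables show that the mechanism works in both directions, not how large it would be in this trial.

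**The case against.** **The phrase may be loose wording.** In a two-page document it could simply mean the usual category of cerclage complications, recorded whatever their cause. On that reading nothing is filtered and the defect is only a missing list. This stands in part: the text describes no case-by-case judgement and names no assessor, so the filter follows from the literal wording, not from a stated procedure. But no fixed category is given either, and under both readings the remedy is the same list.

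**Events called unrelated are not lost altogether.** A reader might infer that they drop out of the trial entirely. The document does not support that. Membrane rupture or infection that ends in miscarriage, early birth or neonatal harm still reaches the randomised comparison through the timing of delivery and the neonatal outcomes. What stays exposed is mainly maternal and procedural morbidity that leaves those outcomes unchanged.

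**The significant example is extreme.** This stands. It needs 100% attribution in one arm and 22% in the other, and 9 v 3 already fails to reach 0.05.

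**The outcome is not the one the trial is sized on, and power for it is low.** Both are true. Even with all events counted, 39 per arm gives only 27% power for 15% v 30%. That limits what the harm comparison can show, but it is no reason to leave an avoidable bias in it.

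**Conclusion.** The concern holds as a risk in the maternal and procedural harm comparison. It rests on two facts in the text, the open-label design and the restriction to related complications, and on the absence of any event list, definition of relatedness or blinded assessor. That unblinded staff would make the attribution is an inference from those facts.

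The size of any bias cannot be derived from the documents. Under the assumed rates, moderate differential attribution (9 v 5 of 39) gives p = 0.38 and only extreme differential attribution (9 v 2) gives p = 0.047. With attribution of 40% v 80%, the chance of a false difference rises from about 3% to between 11% and 20%.

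A reader might also infer that the efficacy result is compromised. It is not: delivery before 34 weeks does not pass through the relatedness filter. The change is worth making because it is cheap and gives a better rule, not because the documents show that bias will occur.

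**What to change.** Replace the restricted outcome with all occurrences, regardless of judged cause, of a pre-specified list of maternal and obstetric complications, counted from randomisation to the end of follow-up. The investigators should settle the list. Candidates are membrane rupture, vaginal bleeding, clinical chorioamnionitis or maternal sepsis, suture displacement, cervical laceration, and bladder or other organ injury. Define each by objective criteria taken from the chart and mark those that occur during the operation. Compare the arms on all listed events. Report relatedness only as a descriptive column, ideally assessed by someone unaware of the arm.

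**Cost.** One changed sentence and a fixed list on the case report form, using data already in the chart. Sample size and treatment do not change.

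**Downsides.** Background events enter both arms, so crude rates rise and harm specific to the procedure is diluted; the intraoperative flag and the relatedness column recover part of that detail. The change removes attribution bias, but some open-label ascertainment bias remains for less objective events such as clinical chorioamnionitis, bleeding and suture displacement, which are still diagnosed and charted by staff who know the arm.

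### Name effect estimates with confidence intervals, and consider Boschloo's test for binary outcomes: Fisher's test is valid with 81.3% power, but about 2 to 5 points more are available at no cost

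*Combined protocol and SAP*

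**What the plan says.** The analysis plan is the short closing paragraph of the combined document. On summaries: "Variables will be described as median, interquartile range or number and percentage". On tests: "The Mann–Whitney test and the Fisher’s exact test will be used for the statistical analysis". On the threshold: "p-values < 0.05 will be considered significant". It does not say whether tests are two-sided. It names no risk difference, risk ratio, difference in gestational age or confidence interval.

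The sample-size paragraph just before it cites an earlier randomised trial in which "the rate of deliveries before 34 weeks of gestation was 53"%, assumes a fall to 20%, and reports that the "size of each group was calculated for 39 patients". The power and any allowance for losses are not given. The outcomes to be analysed include "The time and mode of delivery", complications and neonatal outcomes. The plan does not state which test goes with which outcome. Fisher's test is taken here as the test for delivery before 34 weeks.

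**The concern.** The trial is meant to compare the efficacy of two techniques, so readers need the size of any difference and its precision as well as a p-value. For binary outcomes, anyone can compute these from the published counts. For time of delivery they cannot: a Mann-Whitney p-value with two medians and two interquartile ranges does not determine how many weeks were gained, nor the interval around that gain.

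The second matter is the binary test. Fisher's test conditions on the total number of events, which makes it conservative in small samples, especially when the arms are exactly equal. An unconditional exact test can use more of the 5% allowance and still guarantee it. At this sample size the choice can decide a borderline result. The two matters are linked: if intervals are added and Fisher's test is kept, the interval will sometimes exclude zero while the p-value stays above 0.05.

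**Working it through.** **Inputs.** From the document: 53% and 20% delivering before 34 weeks, 39 per group, significance threshold 0.05. Assumed because not stated: two-sided testing, 80% target power, no losses.

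**1. Reproducing 39 per group.** The uncorrected formula for two proportions, with mean rate p̄ = (0.53 + 0.20)/2 = 0.365, is

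n = [1.960·√(2 × 0.365 × 0.635) + 0.842·√(0.53 × 0.47 + 0.20 × 0.80)]² / 0.33² = 32.2, rounded up to 33.

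The continuity correction gives (32.2/4)·[1 + √(1 + 4/(32.2 × 0.33))]² = 38.02, rounded up to 39. This is the plan's figure.

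**2. Fisher's test at 39/39.** All 40 × 40 outcome tables were enumerated, each weighted by its binomial probability.
- Power at 53% versus 20%: 81.3%.
- Type I error at common rates of 20%, 30%, 36.5%, 50% and 53%: 2.76%, 2.75%, 2.72%, 3.08% and 3.05%. The maximum over all common rates is 3.08%.

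**3. Boschloo's test at 39/39.** The tables are ordered by the two-sided Fisher p-value. The cut-off is then raised as far as possible while type I error, maximised over the common rate, stays at or below 5%. The cut-off becomes 0.0690 and the maximum type I error 4.95%. Because 0.0690 is above 0.05, every table that Fisher's test rejects is also rejected here.

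**4. Power under other conditions** (first arm at 53%):

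| Arms | Second arm | Fisher | Boschloo | Gain (points) |
|---|---|---|---|---|
| 39/39 | 20% | 81.3% | 86.5% | 5.2 |
| 36/42 | 20% | 84.3% | 86.5% | 2.2 |
| 37/41 | 20% | 84.2% | 87.9% | 3.7 |
| 38/40 | 20% | 83.7% | 86.8% | 3.1 |
| 40/38 | 20% | 85.6% | 87.4% | 1.8 |
| 41/37 | 20% | 84.3% | 86.4% | 2.0 |
| 42/36 | 20% | 83.4% | 86.9% | 3.6 |
| 35/35 | 20% | 77.5% | 82.7% | 5.2 |
| 39/39 | 30% | 45.6% | 54.3% | 8.7 |

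Gains are taken from unrounded powers. At the unequal splits Fisher's maximum type I error is 3.9% to 4.2%, which is why less is gained there. At 53% versus 30% the gain at those splits is 1.2 to 3.4 points.

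**5. A borderline table.** With 20/39 (51.3%) versus 11/39 (28.2%), Fisher's p is 0.063 and Boschloo's 0.041. The risk difference is 23.1 points (Miettinen-Nurminen 95% interval 1.2 to 42.9) and the risk ratio 11/20 = 0.55 (0.30 to 0.97).

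**6. Agreement of interval and test at 39/39.** The probability that the Miettinen-Nurminen interval excludes zero while the test is non-significant:

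| True rates | Fisher | Boschloo |
|---|---|---|
| 53% vs 20% | 5.6% | 0.4% |
| 53% vs 30% | 9.3% | 0.6% |

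**7. Time of delivery.** In constructed samples of 39 per arm, identical summaries (median 33, quartiles 26 and 37 weeks, versus median 36, quartiles 31 and 38) are compatible with a Hodges-Lehmann difference of −0.4 weeks (95% interval −2.3 to 2.4; Mann-Whitney p = 0.75) or 4.3 weeks (2.1 to 7.9; p = 0.0002). Only the spacing of values between the quartiles differs.

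**The case against.** The strongest reply is that nothing needs repair. Fisher's test is valid, widely understood, and reaches the assumed 80% power at the planned size, so replacing it is a preference. That is right as far as it goes: this is an improvement, and another unconditional exact test would serve equally well.

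The largest gain also depends on exactly equal arms, which the document does not guarantee because it describes no allocation method. With 38/39, Fisher's power is already 84.3% and the gain falls to 2.9 points. This stands, and is why the gain is given as about 2 to 5 points.

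The borderline table is a selected one. With 20/38 versus 11/39 both tests are significant (0.038 and 0.032), and at 39/39 moving one event can bring them back into agreement. It shows what can happen, not what usually will. The constructed delivery-time samples likewise prove that the summaries are insufficient, without measuring how much information would typically be lost.

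Finally, the trial is multicentre, and Boschloo's test serves only an unadjusted two-by-two comparison. A centre-stratified or adjusted analysis would not use it. That limits the second recommendation and leaves the first untouched. It is also true that the plan does not exclude estimates and intervals. But an estimate chosen after the results are known is weaker than one named in advance.

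**Conclusion.** The point holds as a recommended improvement, not an error. The reporting gap matters more: no effect estimate or interval is named, and for time of delivery readers could not recover one from the planned summaries. Changing the binary test is worth 5.2 points of power at the design rates with 39/39 and 1.8 to 3.7 points at splits from 36/42 to 42/36, with type I error still held at 5%. With 35 evaluable women per arm, Fisher's power falls below 80% (77.5%) and Boschloo's does not (82.7%).

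These figures assume two-sided 5% testing, Fisher's test as the analysis of delivery before 34 weeks, and no adjustment for centre. A better test does not rescue an optimistic effect: at 53% versus 30%, power at 39/39 is 45.6% or 54.3%.

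**What to change.** Before outcomes are compared by arm, add to the SAP:

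1. For every binary outcome, the risk difference and risk ratio with 95% confidence intervals, for example Miettinen-Nurminen. For gestational age at delivery, the Hodges-Lehmann difference with its 95% interval.
2. A statement that tests are two-sided at 0.05.
3. For unadjusted binary comparisons, Boschloo's exact test ordered by the two-sided Fisher p-value, with Fisher's test as a sensitivity analysis.

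If the sponsor prefers to keep Fisher's test, items 1 and 2 still stand. The SAP should then say in advance how a disagreement between interval and p-value will be read.

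The cost is a few sentences of wording and standard software, with 39 per arm unchanged. The drawbacks are that Boschloo's test is less familiar to clinical readers and does not extend to a centre-adjusted analysis. The timing is essential, because a change of test made after a borderline table has been seen would not be credible.
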